2.3.2.5 Treated Target Joint Bleeds

Target joints are joints into which repeated bleeds occur (i.e., ≥ 3 bleeds into the same joint over the last 24 weeks prior to study entry). The target joints prior to study entry are identified through the eCRF. The bleeds in target joints during the efficacy period are defined by first selecting the bleeds that fulfill the definition of a treated joint bleed and then counting how many of these occurred in a target joint as defined prior to study entry. The locations to be taken into account are shoulder, elbow, wrist, fingers/thumb, hip, knee, ankle, sole/heel, and toes. Left and right sides of the same joint type are considered to be separate joints.

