2.2 EXPANSION PHASE

2.2.1 Efficacy Objectives

The efficacy objectives are as follows:

- To evaluate the efficacy of prophylactic emicizumab in maintaining adequate control of bleeding
- To evaluate the clinical effect of prophylactic emicizumab on the number of joint bleeds over time
- To evaluate the clinical effect of prophylactic emicizumab on the number of target joint bleeds over time (target joints are defined as joints with ≥ 3 bleeds occurring in the same joint over the last 24 weeks prior to study entry)
- To evaluate the clinical effect of prophylactic emicizumab on the number of all bleeds (i.e., those treated and untreated with coagulation factors) over time
- To evaluate the clinical effect of prophylactic emicizumab on the number of spontaneous bleeds over time (spontaneous bleed rate)

- To evaluate the HRQoL of patients according to Haem-A-QoL ($\geq 18y$) or Haemo-QoL_SF (ages 12–17) scores after 24 weeks
- To evaluate the health status of patients according to EuroQoL 5-Dimension, 5-Level Questionnaire (EQ-5D-5L) scores after 24 weeks
- To assess preference for emicizumab regimen compared with previous regimen used
- To assess the number of days away from school/work
- To assess the number of days hospitalized

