4.5.8 Bleed Definitions

Definition of a Bleed

For the purpose of the efficacy analyses, a standardized definition of bleed, adapted from criteria defined by the Subcommittee on Standards and Criteria, FVIII/FIX subcommittee of the International Society of Thrombosis and Hemostasis, and similar to that used in a recent clinical study, will be utilized in this study (Blanchette et al. 2014; Mahlangu et al. 2014).

- An event is considered a bleed if coagulation factors are administered to treat signs or symptoms of bleeding (e.g., pain, swelling, etc.). An additional definition of all reported bleeds (irrespective of treatment with coagulation factors) will be applied for a separate analysis.
- Bleeds starting from the first sign of bleed and ending 72 hours after the last treatment for the bleed, within which any symptoms of bleeding at the same location or injections are ≤ 72 hours apart, are considered the same bleed.
- Any injection to treat the bleed, taken > 72 hours after the preceding injection, is considered the first injection to treat a new bleed at the same location.
- Any bleed at a different location is considered a separate bleed regardless of time from last injection.

Definitions of Bleed Sites

- Target joints: defined as a major joint (e.g., hip, elbow, wrist, shoulder, knee, and ankle) into which repeated bleeds occur (frequency of ≥ 3 bleeds into the same joint over the last 24 weeks prior to study entry)
- Joint bleeds are defined as bleeds with bleed type “joint bleed” reported via the bleed/medication questionnaire with at least one of the following symptoms:
 - Increasing swelling or warmth of the skin over the joint
 - Increasing pain
 - Progressive loss of range of motion or difficulty in using the limb as compared with baseline
- Muscle bleeds (sites as per the bleed/medication questionnaire)
- Other (sites as per the bleed/medication questionnaire)

Definitions of Bleed Types

In addition, the assessment of a bleed will be separated into spontaneous bleeds, traumatic bleeds and bleeds related to procedure/surgery. Both spontaneous bleeds (i.e., the occurrence of hemorrhage where neither the patient nor a caregiver can identify a reason) and traumatic bleeds (i.e., hemorrhage occurring secondary to an event such as trauma, “strenuous” activity, or “overuse”) will be collected.

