4.5.3 Subgroup Analyses

Additional descriptive summaries of both treated bleeds and all bleeds will be computed for various subgroups of the study. The summaries will include subgroup ABR and its 95% CIs. The main pre-specified subgroups are as follows:

- Age: <18, ≥18
- Age: <65, ≥65

- Race: Asian, Black or African American, White, Other
- Hemophilia severity: mild, moderate, severe
- Number of target joints at study entry: no target joint, any target joint
- FVIII Inhibitor status: with FVIII inhibitor, without FVIII inhibitors
- Previous treatment regimen: prior episodic, prior prophylactic
- Number of bleeds in the 24 weeks prior to entry: $<9, \geq 9$ for patients being on prior episodic treatment

Note that due to the likely small sample sizes, subgroup analyses will be highly susceptible to variability and should therefore be interpreted with caution.

Additional region- and/or country-specific analyses may be performed to support regulatory submissions as needed.

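### SAP 2.3.2.5 lists fingers/thumb, sole/heel and toes as target-joint locations, although protocol 4.5.8 limits target joints to major joints

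*SAP*

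**What the plan says.** Protocol 4.5.8 says that a target joint is "defined as a major joint (e.g., hip, elbow, wrist, shoulder, knee, and ankle) into which repeated bleeds occur", with at least 3 bleeds into the same joint in the 24 weeks before study entry. Protocol 2.2.1 has a shorter version without the word major: "target joints are defined as joints with ≥ 3 bleeds occurring in the same joint". The protocol synopsis and SAP 2.3.2 repeat the short version.

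SAP 2.3.1 refers to protocol 4.5.8 for its bleed criteria and presents the sections that follow as the more specific rules. Among these, SAP 2.3.2.5 starts from "Target joints are joints into which repeated bleeds occur", keeps the rule of 3 bleeds in 24 weeks, and then lists the locations: "shoulder, elbow, wrist, fingers/thumb, hip, knee, ankle, sole/heel, and toes". It adds that "Left and right sides of the same joint type are considered to be separate joints" and that "The target joints prior to study entry are identified through the eCRF". The endpoint counts on-study treated joint bleeds that fall in a target joint identified before entry.

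The same concept is used twice more. SAP 4.4 summarises the number of target joints at baseline. SAP 4.5.3 names a subgroup, "Number of target joints at study entry: no target joint, any target joint", for which treated-bleed and all-bleed ABRs with 95% CIs are reported. Neither section gives its own definition.

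**The concern.** SAP 2.3.2.5 reads as the operational form of protocol 4.5.8, yet it is wider and does not say so. On an ordinary reading, digits are not major joints, and sole/heel is a region of the foot rather than a named joint. A programmer who follows the SAP list could count target-joint bleeds that protocol 4.5.8 excludes.

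Bleeding into target joints is a stated efficacy objective. The same definition may also decide who is described as having a target joint at entry and who enters the corresponding subgroup. With 40 patients in the expansion cohort, a reclassified patient or two would be visible in those tables.

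**Working it through.** No figure in the plan depends on this definition. The sample size rests on clinical considerations and there is no hypothesis test. The check is a comparison of the location lists.

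**Locations**

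| Source | Restricted to major joints? | Locations |
|---|---|---|
| Protocol 4.5.8 | Yes | hip, elbow, wrist, shoulder, knee, ankle (examples) |
| Protocol 2.2.1, SAP 2.3.2 | No | none listed |
| SAP 2.3.2.5 | No | the same six, plus fingers/thumb, sole/heel, toes |

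With left and right counted separately, the six protocol examples give 6 × 2 = 12 sites. The SAP list gives 9 × 2 = 18 sites. The difference is 3 locations, or 6 sites.

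**Direction.** All six protocol examples are in the SAP list. If those six are taken as the major joints, every protocol target joint is also a SAP target joint, and the reverse need not hold. For the same patient and the same bleeds:

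- target joints (SAP) ≥ target joints (protocol 4.5.8);
- target-joint bleeds (SAP) ≥ target-joint bleeds (protocol 4.5.8);
- patients with any target joint (SAP) ≥ patients with any target joint (protocol 4.5.8).

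The subgroup ABRs have no fixed direction, because a patient who moves may bleed more or less than those already in either group.

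**When the bleed count is strictly larger.** Two conditions must both hold for some patient:

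1. A target joint at fingers/thumb, sole/heel or toes is recorded on the eCRF, with at least 3 bleeds in the 24 weeks before entry.
2. On study, a treated bleed occurs at that location and meets SAP 2.3.2.4, that is, it is reported as a joint bleed with at least one of the listed symptoms.

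The baseline count and the subgroup need only the first condition.

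**Size.** The documents give no bleed data by location, so the size has to be assumed. Let k be the number of the 40 expansion patients whose only target joint is at an extra location. The share that moves to the group with any target joint is k/40:

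- k = 0: 0/40 = 0 percentage points
- k = 1: 1/40 = 2.5 percentage points
- k = 2: 2/40 = 5 percentage points

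**The case against.** The best counter-argument is that the SAP agrees with the protocol's own objectives. Protocol 2.2.1 speaks only of joints, and SAP 2.3.2 carries that wording over. This stands to the extent that part of the inconsistency is inside the protocol, and correcting SAP 2.3.2.5 alone would leave it there. It does not remove the conflict, because 4.5.8 is the protocol's definition section and the one to which SAP 2.3.1 refers.

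The protocol list is also introduced as a set of examples and is therefore open. But the examples illustrate major joints, and an open list does not stretch that term to digits or to a region of the foot. Closing the list at six is a choice that should be stated as one.

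Four stronger readings are tempting, and the documents do not support them:

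- *The SAP list changes who has a target joint at entry.* Baseline target joints come from the eCRF, whose location coding is not shown. In SAP 2.3.2.5 the list follows the sentence on counting on-study bleeds, so it may govern only that step. The baseline and subgroup effect is conditional.
- *Three bleeds in three digits of one hand would make a target joint.* The SAP still requires the bleeds to be in the same joint and does not say that the digits are pooled. The text leaves this open but does not prescribe it.
- *Any sole or heel bleed would be counted.* A bleed reported as muscle or other fails the treated joint bleed definition before location is considered.
- *The SAP departed from the protocol text it was written against.* The SAP appends the version 2 synopsis, the protocol supplied is version 5, and version 2 of Section 4.5.8 is not available. The origin of the difference cannot be traced.

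**Conclusion.** The mismatch is real and is certain at the level of the text: nine locations in SAP 2.3.2.5 against major joints only in protocol 4.5.8. Under the SAP rule the target-joint bleed count can stay the same or rise relative to protocol 4.5.8, but cannot fall, if the six examples are taken as the major joints.

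An effect on the baseline target-joint count and on the subgroup depends on the eCRF recording target joints at the extra locations. On the assumption of 0 to 2 such patients among 40, it is 0 to 5 percentage points and may be zero.

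The point is minor. All efficacy analyses are descriptive, SAP 4.5.3 already advises caution with small subgroups, and the key treated-bleed analysis and the sample size are unaffected. It is still worth correcting, because it concerns the counting rule of a stated endpoint.

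**What to change.** 1. In SAP 2.3.2.5, restrict target-joint locations to the major joints as in protocol 4.5.8: shoulder, elbow, wrist, hip, knee and ankle, with left and right separate.
2. Apply that list to the baseline target joints (SAP 4.4), the target-joint bleed endpoint and the SAP 4.5.3 subgroup, and say so in the text.
3. State that bleeds of type joint in the fingers or toes remain in the treated joint bleed, treated bleed and all-bleed counts where they meet those definitions. Only the target-joint count excludes them.
4. Align the short definition in protocol 2.2.1 and SAP 2.3.2 with protocol 4.5.8.
5. If the wider list is intended, declare it as a deviation from protocol 4.5.8 and add a summary limited to the six major joints.

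The cost is one line in SAP 2.3.2.5, the matching derivation, and wording changes elsewhere. Protocol 4.5.2 already requires the type and location of bleeds in the 24 weeks before entry, so no new data should be needed, subject to confirming how the eCRF codes location.

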2.3.3 Health-Related Quality-of-Life (HRQoL) Endpoints

The EQ-5D-5L index utility score using the U.K. value set and visual analog scale (VAS) will be evaluated.

Because different measures, Haem-A-QoL and Haemo-QoL-SF, are used for the adult and adolescent patients, respectively, all calculations and analyses will be conducted

separately for these two measures. For either questionnaire, descriptive analyses including summaries and 95% CIs of change from baseline for each individual subscale and the overall score will be performed.

Proportion of patients preferring emicizumab after 17 weeks of treatment will be presented along with ranked reasons for that choice.

Summary statistics of the number of days away from school/work and days hospitalized will be presented. Number of days of missed daycare/school and days hospitalized will be analyzed using descriptive statistics and 95% CIs.

2.3.4 Pharmacokinetic Endpoints

The PK endpoint for this study is the exposure (C_{trough}) of emicizumab prior to drug administration at the following timepoints:

PK Run-In Cohort

- Week 1 (predose Day 1; 8 hours post-injection on Day 1; then Day 3, Day 5); Week 2 (Day 8, Day 11); Week 3 (Day 15, Day 18); Week 4 (Day 22); Week 5 (Day 29 predose); Week 6 (Day 36); Week 7 (Day 43); and Week 8 (Day 50)
- Week 9 (Day 57); Week 13 (Day 85); Week 17 (Day 113); and Week 21 (Day 141) and additionally, once between two emicizumab administrations occurring between Week 9 and Week 21
- Week 22 (Day 148); Week 23 (Day 155); Week 24 (Day 162); and Week 25 (Day 169)
- Every 12 weeks, thereafter, while on emicizumab, until the end of the study.

Expansion Cohort

- Every week during Weeks 1–4 on emicizumab
- Every 4 weeks during Weeks 5–25 on emicizumab
- Every 12 weeks, thereafter, while on emicizumab, until the end of the study.

2.3.5 Safety Endpoints

Safety parameters to be measured include exposure, adverse events (including serious adverse events, adverse events of special interest, adverse events leading to drug discontinuation, and deaths), clinical laboratory results (hematology, chemistry, and anti-emicizumab antibodies), vital signs, ECG, concomitant medication use, and incidence of de novo development of FVIII inhibitors (in the non-inhibitor population).

2.3.6 Biomarker Endpoints

Biomarker endpoints include standard aPTT, modified aPTT, PT and prothrombin time international normalized ratio, D-Dimer, peak height thrombin generation, FIX antigen, FXIII activity, FVIII inhibitor titer, FVIII activity, fibrinogen, and pro-thrombin fragment 1.2 vWF antigen.

2.4 DETERMINATION OF SAMPLE SIZE

The sample size of 6 patients for the PK run-in cohort is considered appropriate to assess pharmacokinetics and safety to allow for an informed decision to open the subsequent expansion cohort with 40 additional patients. One additional patient was recruited in the run-in cohort to ensure that the predefined number of patients (6) complete 6-weeks treatment for required PK data in order to enable a decision for opening the expansion cohort, in case of withdrawal.

The overall sample size of 40 patients in the expansion cohort is based primarily on clinical considerations taking into account the limited number of patients with hemophilia A. It is expected that a sample size of 40 patients would, nonetheless, provide statistically robust point estimates with meaningfully narrow CIs.

2.5 ANALYSIS TIMING

Analysis on the PK run-in cohort will be conducted 6 weeks after the first 6 patients have completed 6 weeks in the study. This analysis will focus on pharmacokinetics and safety to inform on the opening of the expansion cohort.

The primary analysis will take place at the earliest time when all enrolled patients in the expansion cohort complete 24 weeks in the study or have withdrawn. These analyses will be carried out separately for patients in the expansion cohort and the PK run-in cohort.

The final analysis will occur at the end of the study as defined in the protocol. Additional updates may be performed between the primary and final analyses, as requested by Health Authorities or deemed necessary by the Sponsor.

Additional analyses for Study BO39182 may be conducted to support regulatory submissions.

3. STUDY CONDUCT

Study BO39182 is a single-arm study implemented in two parts. The first part enrolled 6 patients to receive 6 mg/kg Q4W of SC emicizumab and will provide pharmacokinetic and safety information for opening of the expansion cohort. An additional seventh patient was enrolled to ensure sufficient patients (6) to complete 6 weeks of treatment for required PK data to make the decision for opening the expansion cohort, in case of a patient withdrawal. Since patients in the run-in cohort do not receive a loading dose and therefore reach steady state concentrations later, their bleeding may not be fully controlled by emicizumab; this cohort is restricted to patients who were previously on episodic treatment.

Forty patients will be enrolled in the expansion cohort to receive prophylactic emicizumab at 3 mg/kg QW loading dose for 4 weeks, followed by 6 mg/kg Q4W.

Patients with either prior episodic or prophylactic treatment regimen are eligible for the expansion cohort.

After 24 weeks in the study, all patients are eligible to up-titrate to 3 mg/kg QW with approval from the Medical Monitor if they fulfill the protocol requirements for up-titration (see Section 4.3.2.1 of the protocol). Subsequently, up-titrated patients may decide to down-titrate to 6 mg/kg Q4W, 3 mg/kg Q2W, or 1.5 mg/kg QW. This process of up- and down-titration may repeat more than once.

3.1 DATA MONITORING

After 6 enrolled patients in the PK run-in cohort have each completed 6 weeks in the study, an analysis will be performed to evaluate PK and preliminary efficacy and safety of prophylactic emicizumab administered subcutaneously at 6 mg/kg/Q4W. This analysis will include data collected from all patients at the time. An internal Roche group will be constituted to evaluate whether or not to open the expansion cohort given the available data. There will not be an independent Data Monitoring Committee (iDMC) or a formal IMC for this study.

4. STATISTICAL METHODS

4.1 OUTPUT LAYOUTS

While the efficacy and safety objectives will primarily be evaluated on the expansion cohort, the same will also be evaluated on the PK run-in cohort at the time of the clinical cutoff to complement the data from the expansion cohort, as applicable. The two key output layouts will therefore be:

- **PK Run-In Cohort:** Includes data from patients enrolled in the PK run-in cohort. This cohort receives 6 mg/kg Q4W without any loading dose.
- **Expansion Cohort:** Includes data from the planned 40 patients who receive 3 mg/kg QW loading dose for 4 weeks followed by 6 mg/kg Q4W.

The output results will be presented in separate tables as below:

| Parameter | Run-In Cohort Total |
|-----------|------------------------|
|-----------|------------------------|

| Parameter | Expansion Cohort Total |
|-----------|---------------------------|
|-----------|---------------------------|

The data under the new, up-titrated or down-titrated dose is analyzed and reported separately. Additional summaries will be produced for key safety and exposure on all data (i.e., data before and after up-titration).

4.2 ANALYSIS POPULATIONS

4.2.1 Treated Patient Population

This population includes all enrolled patients who received at least one dose of emicizumab. This will be the primary efficacy and safety analysis population separately for PK run-in and expansion cohorts as described above.

4.2.2 All Patient Population

This population includes all patients enrolled into the study.

4.2.3 Pharmacokinetic-Evaluable Population

This population includes all patients who have received at least one dose of emicizumab and have at least one post-dose emicizumab concentration result.

4.2.4 Up-Titrated/Down-Titrated Population

This population includes patients whose dose was changed at least once during the study.

4.3 ANALYSIS OF STUDY CONDUCT

The flow of patients through the study will be displayed in a “CONSORT” diagram. A clear account of all patients who entered the study, were enrolled, and completed the study will be displayed. In addition, reasons for premature discontinuation from study treatment and reasons for withdrawing from the study will be described.

Major protocol deviations will be summarized.

Observation time and duration of follow-up, as well as adherence to schedule of assessments and compliance with data entry into the electronic, handheld device will also be evaluated.

4.4 DEMOGRAPHICS AND BASELINE CHARACTERISTICS

Demographic data (e.g., age, race/ethnicity, height, weight) and baseline disease characteristics (e.g., inhibitor status, previous hemophilia treatment, number of target joints) will be summarized for all patients.

4.5 EFFICACY ANALYSIS

Efficacy objectives in this study will be assessed descriptively without any formal hypothesis testing.

4.5.1 Bleed Rate Endpoints

The number of bleeds will be analyzed using the negative binomial regression model with efficacy period as an offset in the model to account for the difference in follow-up times. Annualized Bleeding Rate (ABR) will be estimated from the model and presented with 95% CI.

In addition to the model based approach, individual patient ABR will also be calculated based on the formula:

$$ABR = \left(\frac{\text{Number of bleeds during efficacy period}}{\text{Number of days during the efficacy period}} \right) \times 365.25$$

Should the negative binomial not converge, then only the formula-based ABR will be presented.

All bleeds will be characterized descriptively, including the type, location, and cause of bleed (surgery/procedure, traumatic, spontaneous). Bleed rates for spontaneous and traumatic bleeds will also be calculated.

The number of bleeds, types, and locations of bleed will be summarized for all patients and listed for each patient individually. Exploratory analyses will be conducted to characterize the type, location, frequency, and pattern of bleeds.

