6.4.1 Efficacy Endpoints

The key efficacy objective is to characterize the efficacy of 6 mg/kg emicizumab Q4W based on the number of bleeds over time for patients in the expansion cohort.

The analyses will be performed using a negative binomial regression model, which accounts for different follow-up times, with the patient's number of bleeds as a function of the time that each patient stays in the study included as an offset in the model.

The number of bleeds will be also annualized (Annualized Bleeding Rate—ABR) for each patient using the following formula:

$$ABR = \left(\frac{\text{Number of bleeds during the efficacy period}}{\text{Total number of days during the efficacy period}} \right) \times 365.25$$

In case the negative binomial model does not converge the above formula will be used as the sole method of analysis.

The clinical effect of prophylactic emicizumab on the number of bleeds, joint bleeds, target joint bleeds, spontaneous bleeds and all bleeds (i.e., those treated and untreated with coagulation factors) over time will be evaluated (see Section 2.2.1).

The number of bleeds, sites of bleeds, and types of bleeds will be summarized for all patients and listed for each patient individually. Several exploratory analyses will be conducted to characterize the type, location, duration, frequency, and pattern of bleeds. For continuous endpoints, descriptive statistics will be calculated and categorical endpoints will be characterized through frequency tables.

The primary final analysis will be performed 24 weeks after the last enrolled patient started treatment or has withdrawn prematurely, whichever occurs first.

A detailed description of the statistical methods that will be used for the efficacy analyses will be provided in the Statistical Analysis Plan.

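### If the negative binomial model fails, the plan drops the follow-up-adjusted bleed rate and its only specified CI; this mainly affects low-count endpoints and small or zero-bleed groups

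*SAP*

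**What the plan says.** SAP 4.5.1 models the number of bleeds by negative binomial regression with the efficacy period as offset, and "Annualized Bleeding Rate (ABR) will be estimated from the model and presented with 95% CI". Separately, "individual patient ABR will also be calculated based on the formula". The contingency rule is "Should the negative binomial not converge, then only the formula-based ABR will be presented". Protocol 6.4.1 has the same rule in stronger terms: "In case the negative binomial model does not converge the above formula will be used as the sole method of analysis".

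Protocol 6.4.1 also provides that "For continuous endpoints, descriptive statistics will be calculated and categorical endpoints will be characterized through frequency tables". That allows a mean or median of the individual ABRs but attaches no interval to it.

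SAP 4.5.3 covers treated bleeds and all bleeds by subgroup: "The summaries will include subgroup ABR and its 95% CIs". It gives no method for these intervals and no rule for a model that fails, though it warns that "due to the likely small sample sizes, subgroup analyses will be highly susceptible to variability".

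Neither document defines non-convergence, names another count model or says what to do when a group has no bleeds.

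**The concern.** The study is descriptive and has no hypothesis test, so the rate and its interval are the efficacy result. Both documents justify the 40 expansion patients by the expectation of robust point estimates and narrow CIs. The fallback removes the interval, and also the offset that the SAP includes to handle unequal follow-up.

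The loss falls in an awkward place. A group with no bleeds has no finite log-rate, so the model cannot give an estimate. The best-controlled groups are therefore the ones reported without an upper limit. The plan contains many groups where counts could be low: target-joint, joint and spontaneous bleeds, several small subgroups, a run-in cohort of 6 or 7, and separate summaries after dose titration.

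**Working it through.** **The plan's own figure.** "The overall sample size of 40 patients in the expansion cohort is based primarily on clinical considerations". No rate, dispersion or CI width is given, so 40 can be neither reproduced nor refuted. The only available arithmetic, 6 + 40 = 46, agrees with the protocol.

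**Inputs from the documents.**
- Follow-up: 24 weeks = 168/365.25 = 0.460 years per patient (SAP 2, 2.5).
- Expansion cohort: 40 patients. Run-in cohort: 6 planned, a seventh enrolled (SAP 2.4, 3).
- Inhibitor patients: ideally 10-12 of about 46 (protocol 3.3.2); 11 is used here.
- Bleed rate: the sponsor's simulations give a median ABR of 1 at troughs of at least 16 µg/mL and 0 at 45 µg/mL or more (protocol 3.3.1). No mean or dispersion is stated.

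**Assumptions.** Mean ABR 0.25 to 2.5; negative binomial dispersion k from 1 to 4 unless stated.

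**Step 1: probability of no bleeds in a group.** P = (1 + kμ)^(−n/k), with μ = ABR × 0.460.
- n = 11, ABR 0.5 (μ = 0.230): k = 1 gives 1.230^(−11) = 0.10; k = 4 gives 1.920^(−2.75) = 0.17.
- n = 6, ABR 1 (μ = 0.460): k = 1 gives 1.460^(−6) = 0.10; k = 4 gives 2.840^(−1.5) = 0.21.
- n = 40, ABR 0.5: below 0.2% for k = 1 to 4.

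A trial fit to an all-zero group stopped with a singular matrix, as expected.

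**Step 2: groups with some bleeds.** Simulated maximum-likelihood fits with a log-time offset (k = 3, follow-up 24-36 weeks, 300 per setting) formally failed to converge in 0-2.3% of simulated groups. More often the fit reported convergence with dispersion near zero or a non-finite standard error: 34% at n = 6, ABR 1; 38% at n = 40, ABR 0.25; 1% at n = 40, ABR 1. With a non-finite standard error, the literal trigger is not met and there is still no interval.

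**Step 3: the key endpoint.** In 200 further fits per setting at n = 40 (k = 3, 168 days), a finite CI was obtained in 198 at ABR 1 and in all 200 at ABR 2.5. At ABR 0.3, 86 of 200 had a non-finite standard error.

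**Step 4: what a fallback interval would give.** With zero bleeds, the upper limit of a two-sided 95% exact Poisson interval is −ln(0.025) = 3.689 divided by patient-years:
- n = 6: 3.689/2.76 = 1.34 per year
- n = 11: 3.689/5.06 = 0.73 per year
- n = 40: 3.689/18.40 = 0.20 per year

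Allowing for overdispersion, solve (1 + kμ)^(−n/k) = 0.025, so the limit is (0.025^(−k/n) − 1)/(k × 0.460). At n = 11 this is 0.87 for k = 1 and 1.54 for k = 4.

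Simulated overall coverage of robust Poisson intervals is about 91-97% at n = 40, and about 85-91% at n = 11, ABR 2.5.

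**The case against.** The strongest reply is that this is a contingency clause that will seldom be used where it matters most. For treated bleeds in 40 patients the model should give a finite CI unless the rate is low, and formal non-convergence in non-zero data is rare. That stands, and it sets the scope of the point.

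Three stronger readings are tempting, and the documents do not support them.

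- **Boundary dispersion as a failure rate.** The sample variance is at or below the mean in about 36-58% of simulated groups at n = 40, ABR 0.3, and 16-39% at ABR 0.5. These are not failure rates: the SAP's trigger is non-convergence, and such fits often converge. At n = 40 even this event occurs in only 2-17% at ABR 1 (k = 1 to 5) and about 1% or less at ABR 2.5.
- **A mean distorted by one short follow-up.** One bleed in a patient who leaves after 7 days is an ABR of 365.25/7 = 52.2, which would add 52.2/40 = 1.30 to a mean of 40. Neither document says the fallback is a mean, a median would hardly move, and no withdrawal rate is given.
- **Subgroup CIs that cannot be delivered.** SAP 4.5.3 does not tie its intervals to the negative binomial model. The accurate charge is an unresolved conflict with 4.5.1 and a missing method. It also covers only treated and all bleeds, not the rarer bleed types.

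Two further limits stand. The efficacy period runs to the clinical cutoff (SAP 2.3.1), so earlier enrollees generally contribute more than 24 weeks and the zero-bleed probabilities lean high. The 10-12 inhibitor patients include the run-in cohort, which is reported separately, so 11 in the expansion cohort is illustrative.

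**Conclusion.** The point holds within that scope. Whenever the model fails, the plan as written gives up the offset-adjusted group rate and the only interval it specifies. Failure is certain in any zero-bleed group: about 10-17% of groups at n = 11 and ABR 0.5, and 10-21% at n = 6 and ABR 1. In other low-count groups the larger problem is a fit that counts as converged but has no usable standard error.

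The exposed analyses are the secondary bleed endpoints, the subgroups, the run-in cohort and the titrated-dose summaries. The key treated-bleed analysis at n = 40 is unlikely to be affected unless the rate is low. No error rate or power is involved; what is lost is the statement of precision. The percentages rest on assumed rates and dispersion and 24 weeks per patient. That failure is certain with zero bleeds does not depend on those assumptions.

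**What to change.** Amend SAP 4.5.1 and protocol 6.4.1, and refer to the rule in SAP 4.5.3:

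1. Define model failure as non-convergence, or a non-finite estimate or standard error.
2. On failure with at least one bleed, report total bleeds divided by total patient-years, with a 95% CI from a Poisson model using the same efficacy-period offset and robust standard errors.
3. With no bleeds, report a rate of 0 with the exact Poisson upper limit.
4. Keep the individual ABRs as a descriptive supplement.

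The cost is a few sentences and a few lines of code; data collection does not change. The downside should be stated in the SAP: these intervals can be too narrow in small or overdispersed groups. Robust coverage is about 85-91% overall at n = 11, ABR 2.5. Among samples whose dispersion estimate is at its boundary it can be lower, about 67-91% at n = 40, ABR 0.5. The zero-bleed limit at n = 11 is 0.73 per year under Poisson, against 0.87-1.54 with dispersion 1 to 4. Label the fallback intervals as approximate and mark in each table where they were used.
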